3.6 Study Outcome Measures

3.6.1 Primary

Volume (mL) of allogenic red blood cells (RBC) transfused intra-operatively.

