7.6.2 Statistical Analysis

Data from the intervention group will be compared to the control group for statistically significant changes. For those outcome measures that result in statistically significant differences between the intervention and control, study investigators will evaluate the numerical values of the differences for clinical significance. Any study outcome measures determined to be clinically significant are considered successful. All outcome measures will be reported for each site individually and for all sites pooled. Note, exact numerical values for clinical significance are not able to be pre-determined for all outcome measures, as the clinical setting and subject population targeted by this investigation are novel and are difficult to predict.

7.6.2.1 Summary Statistics and Baseline comparisons:

Descriptive statistics will be estimated for each group. Continuous variables will be described by their means, medians, standard deviations, and interquartile ranges. Categorical variables will be described by their frequencies and percentages. Demographics and baseline clinical measurements will be compared

Evaluation of Impacts of Continuous Non-Invasive Intra-operative Hemoglobin and RPVi Monitoring on Intra-operative and Post-Surgical Clinical Outcomes

BIGT0001 version 2

between the groups using ANOVA to compare the means of the continuous variables and Fisher's exact test / Pearson's chi-squared test (χ^2) to compare the rates of the categorical variables.

7.6.2.2 Study Outcomes Statistical Analysis:

Having measurements collected within clusters (clinical site) creates correlated observations. These correlations invalidate the independence assumption in commonly used univariate and multivariate statistical techniques such as t-tests and multiple linear regression. Generalized Linear mixed models (GLMMs) are a flexible class of models that account for correlated observations and thus are a commonly used method for cluster data analysis. This class of model does not require the normality assumption. Generalized linear mixed models will be used for outcomes following a distribution from the exponential family other than normal.

GLMMs will be used to assess the effect of the intervention on continuous and discrete dependent variables. GLMMs differing with respect to their fixed effects, random effects, and residual covariance matrix will be examined. GLMM generally take the form of Equation 1 for baseline observations.

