Equation 1. Generalized Linear mixed model assessing intervention effect for a given outcome:

$$y_{ij} = (\beta_0 + \gamma_{0j}) + \beta_1 * \text{intervention} + \sum_{k=2}^p \beta_k x_k + \varepsilon_{ij} \quad (1)$$

The outcome, y_{ij} is the value of a response variable for the i^{th} individual of the j^{th} cluster (clinical site).

The betas represent fixed effects for the intercept (β_0), intervention coefficient (β_1), as well as coefficients (β_2, \dots, β_p) for other variables to be included in the model (e.g. demographic and clinical variables). The gamma coefficient (γ_{0j}) represents a cluster-specific random intercept. It is assumed that γ_{0j} has a normal distribution with a mean of zero and a variance of $\sigma_{\gamma_0}^2$.

Type III tests will be used to test the null hypothesis that a specific fixed effect equals zero ($H_0 : \beta_k = 0$). Wald z-tests will be used to test for a significant random intercept ($H_0 : \sigma_{\gamma_0}^2 = 0$). Residual and influence diagnostics will be assessed for all models.

Sequential boundary tolerances will be estimated using Lan & DeMets alpha spending function approach. Statistical analysis will be performed using SAS 9.4 (SAS Institute, Cary, NC)

Table 6. Aims, Outcome Measures and Associated Analysis Planned for those Aims.

Aims/Objectives	Outcome Measures	Planned Statistical Analysis
Reduce overall allogenic transfusion - Volume	Volume of allogenic RBC transfused: Intra operatively	Binomial-Gamma hurdle model. We will include intervention group, demographic and clinical data in the model as progresses.
	Volume of allogenic RBC transfused: Post operatively	

Evaluation of Impacts of Continuous Non-Invasive Intra-operative Hemoglobin and RPVi Monitoring on Intra-operative and Post-Surgical Clinical Outcomes

BIGT0001 version 2

Evaluation of Impacts of Continuous Non-Invasive Intra-operative Hemoglobin and RPVi Monitoring on Intra-operative and Post-Surgical Clinical Outcomes

BIGT0001 version 2

Aims/Objectives	Outcome Measures	Planned Statistical Analysis
[REDACTED]	[REDACTED]	[REDACTED]
	[REDACTED]	
	[REDACTED]	
	[REDACTED]	

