7.8 Interim Analysis decisions

The interim analysis will be performed after collecting data on 281 subjects in the intervention group and 562 subjects in the control group.

The Lan-DeMets bounds using O'Brien-Fleming spending function was utilized to calculate the spending alpha. The Overall alpha is 0.05 and One-Sided Bounds

Table 7. Adjusted Alpha and Boundary Results

Analysis	Time	Upper Boundary	Adjusted Alpha	Cumulative Alpha
Interim	0.5	2.5380	0.0056	0.0056
Final	1	1.6621	0.0444	0.0500

Interim Analysis results will be presented to the principal investigators, the sponsor, and the DSMB for evaluation and decision-making.

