7.9 Early Stopping Rules

- Upon review of occurrence of unanticipated adverse device effects and/or other harmful events as a direct result of the clinical investigational procedures, principal investigators, sponsor, and DSMB may decide to terminate the study to safeguard subject safety.
- If the results of the interim analysis show a statistically significant result relating to the outcome measures, then the principal investigators, sponsor, and DSMB may decide to terminate the study.

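### The success wording in 7.6.2 and the efficacy stopping rule in 7.9 are not limited to the one primary outcome, while Table 7 spends a single one-sided 5%

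*Combined protocol and SAP*

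**What the plan says.** Sections 3.5.1 and 3.6.1 give one primary objective and one primary outcome: "Volume (mL) of allogenic red blood cells (RBC) transfused intra-operatively".

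Section 7.8 sets the error rate: "The Overall alpha is 0.05 and One-Sided Bounds". Table 7 spends it over two looks, with bounds 2.5380 at time 0.5 and 1.6621 at time 1. Section 7.8 does not name the outcome that the bounds govern.

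Section 7.6.2 describes two steps. The first is statistical: "For those outcome measures that result in statistically significant differences between the intervention and control", the investigators go on to judge clinical importance. The second ends: "Any study outcome measures determined to be clinically significant are considered successful". No alpha and no order of testing is given there. The section adds that thresholds for clinical significance cannot be fixed in advance for every outcome.

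Section 7.9 has the efficacy stopping rule. Its trigger reads: "If the results of the interim analysis show a statistically significant result relating to the outcome measures". Whether to stop at that point is left to the discretion of the investigators, the sponsor and the DSMB. The rule names neither the primary outcome nor a boundary.

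Within section 7, outcome measures are more than the primary. The readable part of Table 6 lists "Volume of allogenic RBC transfused: Post operatively" in its outcome column, and section 6.6 says that the 30-day call serves secondary outcome measures.

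**The concern.** A single alpha-spending plan controls the error of a single test. Sections 7.6.2 and 7.9 attach consequences (a success label, permission to stop) to any outcome in a longer list, and no readable text allocates error across that list. Two things are at stake.

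- **False positives.** With several chances to be significant, the chance that at least one outcome is significant by luck exceeds 5%.
- **Loss of the primary test.** This needs no false positive. If a real effect on another outcome ends the trial at the interim, the primary is left with partial information and may stay unproven although the effect exists. This cannot be repaired afterwards.

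**Working it through.** **Inputs from the plan.** One-sided alpha 0.05 with Lan-DeMets O'Brien-Fleming spending (7.8); bounds 2.5380 and 1.6621 (Table 7); interim at 281 + 562 = 843 subjects (7.6.1, 7.8); total about 2304 (3.1, 5.1).

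**Assumptions.** Two outcomes may count, the smallest number that the readable Table 6 supports. Their correlation r is 0, 0.5 or 0.8. Both are held to the Table 7 bounds. Power for the primary is 80%, because the plan's figure is not readable.

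**Step 1: reproduce Table 7.** The spending function is alpha(t) = 2[1 − Φ(1.960/√t)]. At t = 0.5 it gives 0.005575, so the interim bound is 2.5380. Solving P(Z1 > 2.5380 or Z2 > c) = 0.05 with correlation √0.5 gives c = 1.6621, and the increment is 0.0500 − 0.0056 = 0.0444. Table 7 is correct for one outcome at t = 0.5.

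**Step 2: false significance with two null outcomes.** At r = 0 the overall figure is 1 − 0.95² = 0.0975, and the interim figure is 1 − (1 − 0.005575)² = 0.0111. For r > 0 a four-variate normal is used (correlation r between outcomes, √0.5 between looks).

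| r | Either outcome, both looks | Either outcome, interim only |
|---|---|---|
| 0 | 9.8% | 1.1% |
| 0.5 | 8.8% | 1.1% |
| 0.8 | 7.5% | 0.9% |
| One outcome (Table 7) | 5.0% | 0.56% |

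**Step 3: power of the primary if the trial always stops when either outcome crosses.** The second outcome is given an equally strong effect. At t = 0.5 a drift of 2.496 gives 80% overall. The interim share is 1 − Φ(2.5380 − 2.496 × 0.7071) = 0.220, which leaves 0.580 for the final look. At r = 0:

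- Only the other outcome crosses at the interim: 0.220 × 0.780 = 0.172.
- Power left for the primary: 0.220 + 0.580 × 0.780 = 0.672.

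**Step 4: the information fraction.** Table 7 uses 0.5, but 843/2304 = 0.366. If information follows subject numbers, the stated bounds give the primary an error of 5.09%. Bounds recalculated at 0.366 are 3.037 and 1.649. Step 3 is repeated for each case:

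| Case | Only the other outcome crosses (r = 0 / 0.5 / 0.8) | Primary power (from 80%) |
|---|---|---|
| t = 0.5, stated bounds | 17% / 12% / 7.5% | 67% / 70% / 73% |
| t = 0.366, stated bounds | 12.9% / 9.3% / 5.9% | 70% / 72% / 75% |
| t = 0.366, recalculated bounds | 5.9% / 4.6% / about 3% | 75% / 76% / 77% |

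If the second outcome has no effect, the loss is under 0.5 points.

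**The case against.** The case against treating this as a serious flaw has five parts.

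- **Section 7.6.2 labels outcomes, not the trial.** A reader might infer that the whole study is declared positive on any one outcome. No sentence says so, and 3.5.1 and 3.6.1 keep a single primary. This stands.
- **Stopping is discretionary.** Section 7.9 permits termination and does not require it, so the power figures describe a mechanical rule that the plan does not contain. This stands as a limit on size. Discretion is not error control, however, and 7.9 gives the decision-makers no criterion that names the primary.
- **No text applies Table 7 to the other outcomes.** Section 7.6.2 gives no alpha, so the familywise figures describe an assumed procedure. They also come before the clinical-significance judgement, which can only lower the rate of declared successes. Both points stand. That judgement has no pre-set threshold for all outcomes, so its effect cannot be calculated.
- **A testing order may be in unreadable text.** Parts of section 7, most of Table 6 and the DSMB Charter are not available. A reader might infer that the plan has no multiplicity control at all, and the documents do not support that. If a hierarchy exists, 7.6.2 and 7.9 as worded do not agree with it and need the same edit.
- **The link from Table 7 to the primary is inferred.** It rests on there being one primary outcome and one set of bounds that spends the full 5%. This stands, and it is a reason to name the outcome in 7.8.

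**Conclusion.** The point holds as a wording fault that should be fixed before the interim. As readable, 7.6.2 and 7.9 allow a success label and an early efficacy stop on outcomes outside the one test that Table 7 appears to cover.

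With two outcomes held to the Table 7 bounds, the chance of at least one false significant result is 7.5% to 9.8% instead of 5%. The loss of primary power is at most about 13 points from an assumed 80% (80 − 67), and about 3 to 5 points (80 − 77 to 80 − 75) with bounds recalculated at 0.366. It arises only with mechanical stopping and a second outcome of equal strength. The readable text does not settle which information fraction applies, so no single figure should be quoted as the expected loss.

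A reader might also infer that Table 7 is wrong, or that the primary's false-positive rate rises to nearly 10%. Neither follows. Table 7 reproduces at its stated time, and the primary's own error stays at about 5% if it is held to those bounds.

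**What to change.** - **7.8:** state that Table 7 applies to intra-operative allogenic RBC volume.
- **7.6.2:** replace the sentence that calls any outcome successful. State that the confirmatory conclusion requires intra-operative allogenic RBC volume to cross its boundary in the direction of reduction, and keep the existing clinical-significance assessment as an additional step.
- **7.9:** limit efficacy stopping to that outcome crossing the Lan-DeMets O'Brien-Fleming bound at the actual information fraction (2.5380 if the fraction is 0.5).
- **Other outcomes:** report them as supportive, or test them in a pre-specified order only after the primary has crossed. If redacted text already holds such an order, cite it in 7.6.2 and 7.9.

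The cost is a few sentences and no added patients. If the fraction at the interim is not 0.5, the bounds must be recomputed. The price is that a non-primary outcome alone can support neither a confirmatory claim nor an early efficacy stop. The change should be made before interim results are seen, because a restriction written afterwards carries less weight.

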3 STUDY DESIGN AND OBJECTIVES

3.1 Overview of the Study Design

Evaluation of Impacts of Continuous Non-Invasive Intra-operative Hemoglobin and RPVi Monitoring on Intra-operative and Post-Surgical Clinical Outcomes

BIGT0001 version 2

This is a sequential, stepped-wedge, controlled, multi-center study with a total enrollment of approximately 2304 subjects across all participating sites (See Figure 1). There will be six clinical sites participating in this study. One interim analysis and one final analysis will be performed.

All control group subjects at each participating clinical site will be enrolled prior to the enrollment of the intervention group subjects. [REDACTED]

The retrospective control group will involve the collection of historical medical records from patients who had undergone similar surgeries as the prospective control and intervention groups. Subjects for the retrospective control group will be selected at random from a list of eligible patients. Refer to Section 5.1.2 Subject Selection Methods for details on selection of the retrospective control subjects.

The prospective control group will be treated as per standard of care. The prospective control group subjects will be given the study device in order to collect In Vivo SpHb and RPVi data during the surgery for post-study analysis; the recorded In Vivo SpHb and RPVi measurements will not be viewable to the investigators, rendering them blinded to In Vivo SpHb and RPVi data during the surgery.

The prospective intervention group will be treated as per standard of care with the addition of non-invasive In Vivo SpHb and RPVi monitoring via the study device as per the procedure stated in the Study Procedure section in this CIP.

Subjects for both prospective control group and intervention group will be enrolled on a convenience sampling basis from hospital patients who are already scheduled for surgery. Refer to Section 5.1.2 Subject Selection Methods for details on selection of the prospective subjects.

Patients' characteristic data such as demographics, skin tone, ASA status, surgery type, etc. will be recorded as part of the study Case Report Form (CRF) and analyzed for comparability between control and intervention groups.

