3.3 Minimization of Potential Bias

Investigator's behavior may be biased due to the Hawthorne/Observer effect. There is the possibility that by simply participating in the study, the investigator may change his/her behavior in terms of blood transfusions because he/she is aware of the study objectives.

By using retrospective controls which establish a historical baseline through chart review and by comparing the blood transfusion patterns/behaviors of the investigators in the prospective control group cases against the retrospective control group cases, possible alteration of behavior by the study investigators from past blood transfusion practice patterns, if any, can be identified and addressed during data analysis.

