6.1.2 Prospective Control Group

Approximately [REDACTED] will be prospective data collection from subjects undergoing surgery. Prospective subjects enrolled in the control arm will be treated per individual clinical site's standard of care (SOC) procedures during and after surgery. The amount of blood transfused, amount of fluid infused, along with other study outcome measures and physiological parameters will be reported on the CRF. In Vivo SpHb and RPVi data will be automatically recorded in the study devices or through a data collection laptop. The display on the study devices will be blacked out so that anesthesiologists will be blinded to the In Vivo SpHb and RPVi monitoring throughout the surgical procedure. All blood transfusion and fluid infusion decisions will be made by clinician's judgment and per SOC procedures. Subjects will receive a phone call from the clinical site staff for a 30-day post-op follow-up on the subject's conditions.

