7.4 Adjusting For Intra-class Correlation

Assuming that the intra class correlation ($ICC = \rho$) is 0.001, the estimated sample size from the simulation is adjusted for the design effect (DE) to account for correlation within each Site.

Adjusted Sample Size = Estimated Sample Size x DE

Where $DE = 1 + (m - 1)\rho$ and m equal to the average estimated sample size per site.

[figure not shown]
Table 5. Sample Size Results

Evaluation of Impacts of Continuous Non-Invasive Intra-operative Hemoglobin and RPVi Monitoring on Intra-operative and Post-Surgical Clinical Outcomes

BIGT0001 version 2

CONFIDENTIAL AND PROPRIETARY
© 2021 Masimo Corporation (Unpublished)
All Rights Reserved

Page 23 of 45

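### Transfusion decisions rest with anesthesiologists, but clustering is prespecified only by site, so the standard error is too small if clinicians differ and their caseload shifts between phases

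*Combined protocol and SAP*

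**What the plan says.** - **Analysis model.** Section 7.6.2.2 argues that "Having measurements collected within clusters (clinical site) creates correlated observations" and that this rules out methods that assume independence. In Equation 1 the only random term "represents a cluster-specific random intercept", and the cluster is the clinical site. For the primary outcome, Table 6 names a binomial-gamma hurdle model with intervention group, demographic and clinical data. Section 7.6.2.2 adds that models with other random effects will be examined, without naming any.
- **Sample size.** Section 7.4 states that the intraclass correlation "is 0.001, the estimated sample size from the simulation is adjusted for the design effect (DE) to account for correlation within each Site".
- **Who decides.** For prospective controls, section 6.1.2 says "All blood transfusion and fluid infusion decisions will be made by clinician's judgment and per SOC procedures". Section 6.2 leaves decisions to the anesthesiologists' clinical judgment, with a transfusion threshold set case by case by the investigator.
- **Clinicians as a source of variation.** Section 3.3 proposes "comparing the blood transfusion patterns/behaviors of the investigators in the prospective control group cases against the retrospective control group cases". Sections 5.1.2 and 5.5 draw retrospective controls from patients of the study anesthesiologists.
- **Order and sampling.** Each site completes its controls before intervention enrollment starts (section 3.1), and prospective patients are a convenience sample (section 5.1.2). No visible text balances anesthesiologists across phases.

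**The concern.** The plan's argument for modelling correlation applies equally one level below the site. Patients of the same anesthesiologist may share that clinician's readiness to transfuse. With only a site intercept, patients within a site are treated as independent given the covariates. If a liberal transfuser handles a larger share of control than of intervention cases, the estimated effect moves, and the standard error does not reflect it. The one-sided error rate could then exceed the planned 5%. Variation between clinicians also stays in the residual, which costs precision.

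**Working it through.** **Plan's own figures.** Section 7.8 says "The Overall alpha is 0.05 and One-Sided Bounds". The Lan-DeMets O'Brien-Fleming-type function at information time 0.5 reproduces Table 7: cumulative alpha 0.0056, bounds 2.5380 and 1.6621. As a single test, 1.6621 has a tail area of 4.8%, which is the benchmark below. The 2304 cannot be rebuilt because its unadjusted input is not visible. It is consistent with about 1779 × [1 + (296.5 − 1) × 0.001] = 1779 × 1.2955 ≈ 2304.7.

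**Inputs from the documents.** Section 3.1 gives "a total enrollment of approximately 2304 subjects across all participating sites" and "There will be six clinical sites participating in this study", so 2304 / 6 = 384 per site. The interim counts of 281 and 562 give a 1:2 split, so n1 = 128 intervention and n0 = 256 control per site. V = 1/128 + 1/256 = 0.01172.

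**Assumed inputs (the documents give none).** K = 6 or 12 anesthesiologists per site; r, the correlation within anesthesiologist inside a site, from 0.01 to 0.10; linear outcome; no true effect. Caseload shares are drawn independently in each phase from a Dirichlet distribution with concentration c = 5 per clinician (milder) or c = 2 (larger). This moves about 22–23% or 34–36% of a site's cases between clinicians.

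**Formula.** Let S be the sum over anesthesiologists of (intervention share − control share)². Then

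true variance / site-only model variance = (1 − r) + r × S/V.

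Chance alone contributes (1 − Σp²)V to S, where p are the underlying shares. This is below V, so the ratio cannot exceed 1 if the shares are the same in both phases. Redrawing the shares adds 2(1 − 1/K)/(Kc + 1) on average. One-sided error is 1 − Φ(1.6621 / √ratio).

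**Example, K = 6, c = 2, r = 0.05.** The redrawn part is 2 × (5/6)/13 = 0.1282, and 0.1282/0.01172 = 10.94. Adding the chance part of 0.77 gives S/V = 11.71. The ratio is 0.95 + 0.05 × 11.71 = 1.535, so the model SE is 19% too small (1 − 1/√1.535) and the error is 9.0%.

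**One-sided error at 1.6621**

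| K | shift | r = 0.01 | r = 0.02 | r = 0.05 | r = 0.10 |
|---|---|---|---|---|---|
| 6 | milder | 5.2% | 5.6% | 6.6% | 8.3% |
| 6 | larger | 5.7% | 6.6% | 9.0% | 12.4% |
| 12 | milder | 5.0% | 5.2% | 5.8% | 6.8% |
| 12 | larger | 5.3% | 5.8% | 7.3% | 9.5% |

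Linear simulations with site in the model agree: in 10,000 trials per setting, 5.1–6.6% at r = 0.02, 5.9–9.3% at 0.05 and 6.9–12.6% at 0.10.

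**A different kind of shift.** Suppose half of K = 10 anesthesiologists are replaced between phases, with r = 0.05. Then S = 0.10 + 0.9V, the ratio is 1.42, and the error at the unadjusted 1.645 is 8.4%. With full replacement the ratio is 1.85 and the error 11.3%.

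**Tying r to the plan's ICC.** Two random patients at a site share an anesthesiologist with probability about 1/K. If the 0.001 includes clinicians, r is at most 0.001 × K, that is 0.006 for K = 6 and 0.012 for K = 12. In the setting of the table the error is then 5.0–5.4%. With complete turnover (K = 10, r = 0.01) the ratio is 1.17 and the error at 1.645 is 6.4%.

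**Effect of adding the clinician.** In linear simulations (3,000 trials per setting), a nested anesthesiologist random intercept brought the error to about 4–5.5% and cut the true SE by 0–27%.

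**The case against.** The strongest reply has five parts.

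- **The model is left open.** A reader might infer that the plan disregards clinicians altogether. It does not go that far: section 7.6.2.2 lets other random effects be examined, so the accurate description is that none is prespecified. A term chosen after looking at the data does not secure the error rate.
- **Some content cannot be seen.** Section 9.8, the detail of sections 7.1 to 7.3 and the sample CRF are withheld or not shown, and the CRF list in section 9.5.2 is not exhaustive. It cannot be claimed that the CRF lacks an anesthesiologist ID. Equation 1 and the primary row of Table 6 are visible and contain no such term.
- **A shift is not shown.** It is tempting to call a change in caseload likely because the phases are sequential. The documents show only that it is possible, and drawing retrospective controls from study anesthesiologists limits turnover. Section 3.3 is about behavior changing under observation; it does not establish stable differences between individuals.
- **The larger ICCs are assumptions.** Values of 0.05–0.10 are well above what 0.001 allows if that figure includes clinicians. This stands.
- **Another remedy exists.** A site-level comparison of phases (t test, 5 df) held the error at about 5% in the linear simulations without clinician data. It would cover the type I error, but it has few degrees of freedom, does not recover precision, and is not prespecified either.

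The design effect of about 1.30 is no answer: it adds patients but does not correct the standard error that the model reports.

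**Conclusion.** The point holds as a conditional one. Clustering is prespecified only by site although anesthesiologists make the decisions. The site-only SE is too small if two things are both true: clinicians differ in transfusion habit, and their case shares differ between phases by more than chance. The documents establish neither. Under the assumed inputs, one-sided error is about 5–6.6% at a clinician ICC of 0.01–0.02, 6–9% at 0.05 and 7–12% at 0.10, against 4.8% nominal. It is not inflated when caseload is the same in both phases. If the plan's 0.001 includes clinicians, it is 5.0–5.4% in this setting and at most 6.4% with full turnover. A reader might infer that the trial's error rate is definitely above 5%; the documents do not support that. All sizes are for a linear outcome, and the hurdle model was not simulated. This is a worthwhile, inexpensive improvement, not a flaw that invalidates the analysis.

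**What to change.** 1. Make sure a coded ID of the anesthesiologist of record is captured in all three groups. The retrospective lists are already built through study anesthesiologists.
2. Prespecify an anesthesiologist-within-site random intercept in both parts of the hurdle model. If the volume part does not converge, use anesthesiologist-clustered standard errors for that part.
3. Before this is fixed in the SAP, check its behavior in the binomial-gamma hurdle model by simulation.
4. Report caseload by anesthesiologist and phase, so that the size of any shift can be seen.

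The cost is at most one CRF field, some SAP wording, a simulation and a slightly heavier model. In the linear simulations the random intercept carried no SE penalty. No clinical procedure changes. The ID is best captured during the trial, since recovering it later would mean going back to the charts.

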1.1 Background and Rationale

Acute and chronic anemia are associated with increased perioperative morbidity and mortality [1-3] Preoperative anemia is reported in many patients scheduled for surgery, with a greater prevalence in older and hospitalized patients.[4] However, transfusion of red blood cells is also associated with morbidity and mortality.[2,5] Evidence based transfusion guidelines are promoted to decrease unnecessary transfusion.[6,7]

Blood management programs are designed to improve patient outcome through preoperative anemia treatment, use of agents that improve hemostasis or clot stability, employing alternatives to transfusion of banked red blood cells, and making individual patient-specific transfusion decisions.[8,9] Despite these programs transfusions are sometimes administered to patients when hemoglobin (Hb) has not decreased to a specified minimum acceptable range (inappropriate transfusion) or is continued after this has increased above the specified target range (excessive transfusion).[10-15] Shander and colleagues estimated that up to two-thirds of transfusions given to surgical patients considered inappropriate in one study.[16]

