3.5.1 Primary

To determine whether the addition of SpHb with In Vivo adjustment and RPVi monitoring using the study device will reduce overall allogenic transfusion, where reduction is defined as the decrease in volume of transfusion of the intervention group relative to control group, intra-operatively.

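### The primary objective is mean transfused mL, but the readable analysis text does not say which effect of the two-part hurdle model is tested, and neither part alone tests volume

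*Combined protocol and SAP*

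**What the plan says.** Section 3.5.1 sets the objective on volume: "reduction is defined as the decrease in volume of transfusion of the intervention group relative to control group, intra-operatively". The outcome in Section 3.6.1 is "Volume (mL) of allogenic red blood cells (RBC) transfused intra-operatively", with no restriction to patients who were transfused.

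The primary row of Table 6 (Section 7.6.2.2) gives the analysis as "Binomial-Gamma hurdle model. We will include intervention group, demographic and clinical data in the model as progresses". It names no contrast and no test.

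The test appears in the general text under Equation 1: "Type III tests will be used to test the null hypothesis that a specific fixed effect equals zero". Equation 1 is a generic mixed model for a given outcome. Its parameters are introduced with "The betas represent fixed effects for the intercept", and it contains a single intervention coefficient.

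Table 7 (Section 7.8) gives one sequence of one-sided bounds, 2.5380 at the interim and 1.6621 at the final analysis, with cumulative alpha 0.0500.

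**The concern.** A hurdle model splits the outcome into any transfusion (binomial part) and volume given transfusion (gamma part). The intervention enters both. One set of bounds needs one Z, and the readable text does not say where that Z comes from. If the general Type III sentence is applied to the hurdle model, the analyst must pick a coefficient. The binomial coefficient asks whether the same share of patients was transfused. The gamma coefficient asks whether mean volume is the same among those transfused, a subset that the intervention itself can change.

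Section 1.1 makes the distinction practical. It names transfusions given before they are indicated, which act mainly on the binomial part. It also names transfusion that "or is continued after this has increased above the specified target range (excessive transfusion"), which acts on the gamma part. A monitor that works through one route can be missed, or read as harm, by a test on the other part. The primary conclusion about mL would then rest on a quantity that is not mL per patient.

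**Working it through.** **1. The plan's own figures.** With one-sided alpha 0.05 and O'Brien-Fleming-type spending at information time 0.5, a(0.5) = 2[1 - Phi(1.960/sqrt(0.5))] = 2[1 - Phi(2.772)] = 0.0056, which gives z = 2.538. The final bound, from the bivariate normal with correlation sqrt(0.5), is 1.6621. Table 7 reproduces. The total of 2304 cannot be rebuilt, because its effect inputs are not readable.

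**2. The algebra.** E[Y] = p x mu, where p = P(Y>0) and mu = E[Y|Y>0]. The log ratio of mean volumes is log(p1/p0) + log(mu1/mu0). A zero in one part means unchanged volume only if the other part is also zero. This needs no assumed figures.

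**3. Inputs for size.**
- From the documents: total 2304; interim 562 control and 281 intervention, which is 2:1; final bound 1.6621; ICC 0.001, so site effects are ignored.
- Assumed: the 2:1 ratio holds at the end (1536:768); 10-40% of controls are transfused; transfused controls receive 1/2/3/4/6/8 units with probabilities .40/.30/.12/.08/.05/.05.
- Mean units = .40 + .60 + .36 + .32 + .30 + .40 = 2.38. Mean square = 8.96, so squared CV = (8.96 - 5.66)/5.66 = 0.582.

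**4. Scenario A: half of one-unit transfusions avoided.** Recipients fall by 20%. Mean if transfused = (2.38 - 0.20)/0.80 = 2.725, up 14.5%. Volume ratio = 0.80 x 2.725/2.38 = 0.916, down 8.4%. At 20% transfused (p0 = .20, p1 = .16; 307.2 and 122.9 recipients; pooled dispersion 0.551):
- Gamma: log(2.725/2.38) = +0.135; SE = sqrt[0.551(1/122.9 + 1/307.2)] = 0.079; Z = 1.71 towards harm. P(crosses for benefit) = Phi(-1.66 - 1.71) < 0.1%. P(crosses for harm) = Phi(1.71 - 1.66) = 52%.
- Binomial: log odds ratio -0.272, SE 0.117, Z = -2.32; power Phi(2.32 - 1.66), about 74%.
- Overall: log(0.916) = -0.088; SE = sqrt[.84/122.9 + .80/307.2 + 0.079^2] = 0.125; Z = -0.70; power about 17%.

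**5. Scenario B: four in five multi-unit recipients get one unit less.** Mean = 2.38 - 0.8 x 0.6 = 1.90, and p is unchanged, so volume is down 20%. At 20% transfused:
- Binomial: true effect zero, so it rejects in Phi(-1.66), about 5%.
- Overall: log(1.90/2.38) = -0.225; pooled dispersion 0.634; SE = sqrt[.80/153.6 + .80/307.2 + 0.634(1/153.6 + 1/307.2)] = 0.118; Z = -1.90; power about 60%.

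**6. Across rates.** The same formulas give:

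| Control rate | A: gamma benefit | A: gamma harm | B: binomial | B: overall |
|---|---|---|---|---|
| 10% | 0.2% | 32% | 5% | 36% |
| 20% | <0.1% | 52% | 5% | 60% |
| 30% | <0.1% | 67% | 5% | 77% |
| 40% | <0.1% | 77% | 5% | 89% |

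Simulation (4,000 trials per cell, final bound only) agrees: gamma benefit at most 0.2%, harm about 31-79%, overall contrast in B about 37-90%.

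**7. Second check.** A simulation with continuous gamma volumes and both Table 7 looks (1,500 trials per scenario) put a true 25% reduction wholly in one part. The test on the other part detected 4.5-6.5%. With a 19% reduction split evenly over both parts at a 20% rate, the overall contrast had 47-55% power, against 30-32% (binomial) and 27-41% (gamma). With volume unchanged, the overall contrast rejected in 4.7-6.3%.

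**The case against.** The Type III sentence is general mixed-model text. It covers any fixed effect, covariates included, and Equation 1 does not describe a hurdle model. A reader might infer that the plan declares a single hurdle coefficient to be the primary test. The documents do not say that; they leave the primary contrast unnamed. This stands and limits the point.

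Sections 7.1-7.5 are largely unreadable, and 9.8 (data processing and analysis) is redacted. Section 7.4 refers to a sample-size simulation, which needed some rejection rule. A combined contrast may be defined there. This also stands.

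A reader might infer that the trial is likely to claim a reduction in mL that did not occur. With 20% fewer transfused and exactly 25% more volume each, the binomial coefficient does reject in about 45-99% of trials. But avoided one-unit transfusions raise the conditional mean by only 14.5%. An exact offset needs the remaining recipients to get about 9% more blood (1.25/1.145 = 1.09), and the documents give no reason to expect that. It is an illustrative worst case. A reader might also infer an error rate near 10% (1 - 0.95^2 = 0.0975). That applies only if success on either coefficient counted, which the plan does not say.

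Section 7.6.2 has investigators judge the numerical differences after significance, so a claimed reduction with equal means would be visible. That review cannot recover a reduction that the test missed.

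Finally, the binomial coefficient does better than the overall contrast in Scenario A. That is true, but it then supports a statement about fewer patients transfused, not about mL.

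**Conclusion.** The point holds for the readable text. Objective and outcome are mean mL over all patients, the model has two intervention effects, and no readable sentence ties one volume contrast to the Table 7 bounds. That neither coefficient alone tests volume is algebra.

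The main consequence is a missed or misread reduction when the effect runs through one part and the test sits on the other: at most 0.2% benefit and about 31-79% harm signals on the gamma part in Scenario A, and about 5% detection on the binomial part in Scenario B against about 37-90% for the overall contrast. These sizes rest on the assumed 10-40% rates, unit distribution and 1536:768 split. If both parts move the same way, each coefficient still points in the right direction. The documents do not establish that the hidden sections lack a combined test.

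**What to change.** Keep the hurdle model. In Section 7.6.2.2 and the primary row of Table 6, name one primary Z: the ratio or difference, intervention against control, of overall mean mL per patient, P(Y>0) x E[Y|Y>0], standardised over the model covariates, with a delta-method or site-stratified bootstrap standard error. State that this Z is compared with the Table 7 bounds at both looks. Report the two coefficients as supportive, and label the gamma part as conditional on being transfused. If an unreadable section already defines such a contrast, a cross-reference from these two places is enough.

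The cost is SAP wording and a post-estimation step, with no new data or patients. The contrast has less power than a single coefficient when the effect lies wholly in that part: about 15-17% against 75-76% in Scenario A at 20% transfused. Any power figure simulated on another statistic must be restated, and the adequacy of 2304 checked against it.
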